14 APPENDIX 2: VISIT WINDOWS

14.1 ECG

The following visit windows will be applied for reporting **ECG** results open-label extension results:

Analysis Timepoint	C017 OLE	
	Target Study Day [1]	Window [2]
		Study Days
Baseline	1	<= 1
Start of OLE [3] – Visit 9	127	>= 113 to <= 141
Visit 12	155	>=142 to <= 323
Visit 16	491	>=324 to <=659
Visit 20	827	>=660 to <= 995
Visit 24	1163	>=996 to <=1306
Visit 28	1499	>=1307 to <=1642
Visit 32	1835	>=1643 to <= 2003
Visit 36	2171	>= 2004 to <=2339
Visit 40	2507	>= 2340 to <= 2675
Visit 44 [4]	2843	>=2676

OLE=Open-label Extension

^[1] Relative to the date of the first dose of study drug. For example, Day 1 = the date of the first dose of study drug.

^[2] The study days evaluated for windows of visits during treatment period are on or prior to the last dose day.

^[3] This window should include the study day when the first dose of OLE study medication was given.

^[4] Expected timepoint C017 OLE.

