The initial target dose for the open-label extension will be 300 mg/day. However, if a subject is not tolerating the 300 mg/day dose, YKP3089 dose may be reduced to a minimum of 50 mg/day. If the investigator feels that a subject requires a dose that is higher than 300 mg/day, the dose can be increased to a maximum of 400 mg/day once the target dose of 300 mg/day was reached. The dose adjustments may occur in weekly increments of 100-mg/day or 50-mg/day. However, the rate of change may be more rapid or slow as clinically indicated. No dose reductions are permitted if the subject is taking 50 mg/day YKP3089. If 50 mg/day YKP3089 is not tolerated, the subject will withdraw from the study. Monotherapy with YKP3089 will not be allowed. The investigator may add, remove, or adjust the dosage of concomitant AEDs, as clinically indicated. In the event of poor tolerability, the investigator may instruct the subject to take the dose of study medication in the evening or divide the total daily dose into 2 doses. Subjects will follow the schedule of study visits and assessments detailed in [Table 2](#). After 12 months of participation in the open-label extension phase, subjects will be re-evaluated. Those who are benefiting from treatment with YKP3089 may continue use of the drug at the discretion of the investigator, until development is stopped by SK Life Science Inc or the product is approved for marketing, or anytime at the discretion of SK Life Science Inc.

6.1.4.3 *Study Drug Taper: Subjects Leaving the Open-Label Extension*

Subjects who are withdrawn from the open-label extension study will taper YKP3089 according to the schedule described in [Table 6](#), unless for safety reasons the investigator judges it necessary to discontinue study drug immediately. The investigator is encouraged to discuss the tolerability criteria with the Sponsor or its designee.

Table 6. Study Drug Taper Schedule for Subjects Completing Open-Label Extension

Final open-label dose of YKP3089 (mg/day)	YKP3089 Dose During Taper (mg/day)		
	Week 1	Week 2	Week 3
50 or 100	None		
150 or 200	100	None	None
250 or 300	200	100	None
350 or 400	300	200	100

The final visit will take place 14 days after the subject's last dose, following taper and discontinuation of YKP3089; at any time during the open-label treatment; or after 12 months of open-label treatment if there is no additional treatment beyond that point.

6.1.5 *Dose Adjustments of Study Drug and Concomitant AEDs*

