As shown in [Table 2](#), the following will be performed at Visit 16 or at the time of early termination from the open-label phase.

At Visit 16, if clinically indicated, the subjects will begin the study drug taper described in Section 6.1.4.3. At the end of this drug taper, the subject will have discontinued YKP3089. The following assessments will be made at Visit 16:

- Record vital signs
- Measure weight
- Conduct full physical examination
- Conduct full neurologic examination
- Administer C-SSRS (Since Last Visit version)
- Perform 12-lead ECG
- Perform urine pregnancy test (for female subjects of childbearing potential)
- Draw blood for laboratory safety assessment
- Obtain urine for urinalysis
- Record concomitant medications
- Perform drug accountability
- Record AEs
- Review seizure diary

For subjects who completed 1 year of open-label treatment:

- Determine whether the subject is benefitting from open-label treatment with YKP3089

For subjects who are benefitting from open-label treatment:

- Dispense open-label medication

- Dispense seizure diary
- Schedule a return to occur in 3 months for next visit
- See section 9.3.9 for further instructions

For subjects leaving the open-label treatment due to any reasons at any time before 1 year or leaving at Visit 16 due to no benefit or any reasons:

- Dispense taper open-label study drug bottles as instructed by IWRS if needed
- Schedule a return to occur in 2 weeks of the last dose for Visit 17 if tapered
- Schedule a return to occur in 2 weeks for Visit 17 if not tapered

9.3.8 ***Visit 17, End of Study Follow-up (14 days from the last dose)***

Visit 17 represents the Follow-up Visit after discontinuation of study drug in the open-label extension phase. This final visit will take place 14 days after the subject's last dose of YKP3089—at any time during the open-label treatment or after 12 months of open-label treatment if there is no additional treatment beyond that point.

As shown in [Table 2](#), the following assessments will be performed at Visit 17:

- Record vital signs
- Measure weight
- Conduct full neurologic examination
- Administer C-SSRS (Since Last Visit version)
- Serum pregnancy test (for female subjects of child-bearing potential)
- Draw blood for laboratory safety assessment
- Obtain urine for urinalysis
- Record concomitant medications
- Perform drug accountability
- Record AEs

No study drug will be dispensed.

9.3.9 *Open-Label Extension Beyond Year One*

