Subjects who complete Visit 16 and will continue in the open-label extension beyond year one will adhere to the following visit schedule. The investigator will schedule a return visit in 3 months. Subjects will have study visits every 3 months for a total of 4 visits per study year. The investigator will perform some or all of the following assessments depending up on the visits.

Perform the following every 3 months from Visit 16

- Record vital signs
- Administer C-SSRS (Since Last Visit version)
- Record concomitant medications
- Perform drug accountability
- Record AEs
- Review seizure diary
- Dispense open-label study drug bottles as instructed by IWRS

Perform the following every 6 months from Visit 16

- Measure weight
- Conduct brief neurologic examination
- Perform urine pregnancy test (for female subjects of childbearing potential)
- Draw blood for laboratory safety assessment

Perform the following every 12 months from Visit 16

- Perform full physical exam
- Perform 12-lead ECG
- Obtain urine for urinalysis

This pattern will continue at the discretion of the investigator until development is stopped by SK Life Science Inc, the product is approved for marketing, or anytime at the discretion of SK Life Science Inc.

After the first year of open-label treatment, the visits will be numbered sequentially beginning with Visit 18.

For subjects who discontinue any time after the first year of the open-label treatment, the subject should be brought to the clinic as soon as possible and the investigator will perform the assessments listed under Visit 16. This visit will be assigned the next sequential number. After this visit, the subject will be scheduled to return for Visit 17 (end-of-study follow-up, 14 days after the last dose of study medication).

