10 SAFETY ENDPOINTS

10.1 Adverse Events

For open-label extension analyses, treatment-emergent AEs are defined as AEs with onset after the start of OLE study medication, up to last dose date of OLE study medication + 30 days, or onset before start of OLE study medication and worsened after starting OLE study medication, up to last dose date of OLE study medication + 30 days.

AE relationship to study drug can be classified by the investigator as definite, probable, possible, remote or unrelated. AEs severity can be rated as mild, moderate or severe.

SAEs will be captured from the time of study drug administration in OLE to 30 days after the last dose of study drug, and will be monitored until resolution or stabilization.

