11.3.2 Analysis of Clinical Laboratory parameters

Laboratory results during open-label extension will be summarized by OLE treatment groups. For these summary tables, results will be reported using visit windows as defined in Appendix 14.2. Shift tables from baseline to each post-baseline OLE visit will be prepared for hematology and chemistry laboratory assessments based on the categories of Low, Normal, and High (for numerical results) or Abnormal and Normal (for categorical results). Baseline measurement is defined as the last available measurement prior to dosing in double-blind.

Laboratory results during OLE will be listed by subject.

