11.3.3 Analysis of Electrocardiograms

All ECG results will be listed on a by-subject basis. ECG parameters consist of heart rate (bpm), PR interval (msec), RR interval (msec), QRS-complex (msec), uncorrected QT interval (msec), and QTcF interval (msec). Individual ECG values (parameters) will be listed by subject and visit. Baseline measurement is defined as the last available measurement prior to dosing in double-blind period.

For summary tables, the following rules will be applied to derive a single value corresponding for this visit:

- For all numerical values, the average of the 3 measurements will be computed
- For qualitative values (normal / abnormal):

SAP-OLE Version Final_15May2021 Page 30 of 43

- If 2 or more results are "abnormal", visit 3 derived results will be "abnormal" (this rule applies for subjects with 3 or 2 measurements)
- Otherwise, visit 3 derived results will be "normal".

For subjects with only one measurement collected at Visit 1 (DB baseline),

the collected value will be used as baseline value for summary results.

For the OLE-SE analysis population the following summary tables will be generated for the ECG data:

- Summary statistics (n, mean, standard deviation, median, minimum, and maximum) of the baseline value, the value at each scheduled postbaseline evaluation, and the corresponding change from baseline for each continuous ECG parameter,
- Count and percentage of subjects with QTcF absolute value > 450 msec, >480 msec, >500 msec, <360 msec, <340 msec, <320 msec, and <300 msec at each scheduled post-baseline evaluation,
- Count and percentage of subjects with a mean change from baseline in QTcF intervals >30 msec, >60 msec >90 msec, <30 msec, <60 msec, and <90 msec at each scheduled post-baseline evaluation,
- Count and percentage of subjects with absolute heart rate > 100 bpm at each scheduled post-baseline evaluation,
- Count and percentage of subjects with heart rate change from baseline >10 bpm, >20 bpm, and >30 bpm at each scheduled post-baseline evaluation,

For these summary tables, results will be reported using visit windows as defined in Appendix 14.1.

ECG results during OLE will be listed by subject.

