11.3.4 Analysis of Vital Signs

All Vital Signs will be listed on a by-subject basis. Baseline measurement is defined as the last available measurement prior to dosing in double-blind period. Vital signs result during open-label phase will be summarized by OLE treatment groups. For these summary tables, results will be reported using visit windows as defined in Appendix 14.3.

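### The open-label visit windows stop at the last dose day and have no termination or follow-up row, so post-dose laboratory, ECG and vital-sign values already collected are left out of the summary tables

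*SAP*

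**What the plan says.** SAP Appendix 2 assigns results to analysis visits by study day. The ECG (14.1), laboratory (14.2) and vital-sign (14.3) tables carry the same footnote [2]: "The study days evaluated for windows of visits during treatment period are on or prior to the last dose day". The rows are baseline, the start of the extension and numbered visits up to Visit 44.

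The analysis sections send the summaries through these windows. SAP 11.3.2 says of the laboratory tables: "For these summary tables, results will be reported using visit windows as defined in Appendix 14.2". It also plans haematology and chemistry shift tables from baseline to every OLE visit after baseline. SAP 11.3.3 says of the ECG tables, which include the QTcF and heart-rate threshold counts: "For these summary tables, results will be reported using visit windows as defined in Appendix 14.1". SAP 11.3.4 says of vital signs: "For these summary tables, results will be reported using visit windows as defined in Appendix 14.3".

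The protocol provides for measurements at and after the end of dosing:

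- **Stopping.** Section 6.1.4.3 has leaving subjects taper "unless for safety reasons the investigator judges it necessary to discontinue study drug immediately". Table 6 in that section gives no taper from a final dose of 50 or 100 mg.
- **Termination visit.** Under 9.3.7 an assessment set that includes vital signs, ECG and laboratory tests "will be performed at Visit 16 or at the time of early termination from the open-label phase". For subjects who discontinue after the first open-label year, 9.3.9 says "the subject should be brought to the clinic as soon as possible" for the same set.
- **Follow-up.** Protocol Table 2 and SAP 10.2 and 10.4 plan laboratory tests and vital signs 14 days after the last dose (protocol Visit 17). No ECG is scheduled then.

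Adverse events have a different horizon. SAP 10.1 counts them as treatment-emergent "up to last dose date of OLE study medication + 30 days".

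**The concern.** A window rule that ends on the last dose day separates subjects by how they stop. A subject who tapers has the termination visit while still dosing, so those results enter a window (if taper doses count toward the last dose day). A subject who stops without a taper and is seen the next day or later contributes nothing from that visit. The planned follow-up results are left out for everyone.

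Shift tables and QTcF counts are where a reader would look for signals the protocol itself reports: a DRESS-type case with eosinophilia and hepatic enzyme abnormalities (4.6), and a mean QTcF shortening of 10 to 15 msec at 300 mg (4.4.4), which is the extension's target dose. A value measured shortly after an untapered stop can bear on either.

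**Working it through.** **1. The rule applied to dates.** The documents give no stopping dates, so the last-dose days here are illustrative: 200, 400 and 600, with results taken 0, 1, 3, 7, 14, 30 and 31 days later. A result is kept only if its study day is on or before the last dose day and falls in a listed window.

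| Result taken | Laboratory | ECG | Vital signs |
|---|---|---|---|
| On the last dose day | kept | kept | kept |
| +1, +3, +7, +14, +30 or +31 days | dropped | dropped | dropped |

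The pattern is the same for all three last-dose days. For example, with the last dose on day 400, a result on day 403 lies inside laboratory Visit 14 (240 to 407), ECG Visit 16 (324 to 659) and vital-sign Visit 15 (366 to 449). Footnote [2] removes it from each because 403 > 400.

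**2. Whether another row catches it.** None does. The vital-sign row labelled Visit 17 has target day 575, which is 491 + 84, an ordinary quarterly visit. It is not the protocol's Visit 17, which is defined by the last dose.

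**3. Against the shift-table plan.** Protocol Visit 17 is an OLE visit with planned chemistry and haematology. SAP 11.3.2 plans a shift to every OLE visit after baseline, yet footnote [2] always excludes this one.

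**4. Where dropped results still appear.**

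- SAP 11.3.2 to 11.3.4 list laboratory, ECG and vital-sign results by subject.
- Protocol 10.1.1 makes an abnormal diagnostic result an adverse event if, for example, it results in study withdrawal. Section 10.2 adds laboratory abnormalities that suggest organ toxicity or require active management.
- Such events are tabulated up to 30 days after the last dose. An event at +3 days is therefore counted, while the value measured that day enters no shift or threshold count.

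**5. How far post-dose values reflect exposure.** Protocol 4.4.2 gives single-dose mean half-lives of 50.2 h (100 mg) to 60.4 h (300 mg). Fraction remaining = 0.5^(t/h):

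| Time after last dose | h = 50.2 | h = 60.4 |
|---|---|---|
| 24 h | 0.72 | 0.76 |
| 72 h | 0.37 | 0.44 |
| 336 h (14 days) | 0.010 | 0.021 |
| 720 h (30 days) | 0.00005 | 0.0003 |

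Values in the first few days still reflect substantial exposure. Values at 14 days are essentially off drug. The two kinds belong in separate rows.

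**The case against.** The case for leaving the SAP alone has several parts.

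- **On-treatment convention.** Footnote [2] speaks of visits during the treatment period, and cutting by-visit summaries at the last dose is ordinary. A longer adverse-event horizon serves a different purpose. This stands: a reader might infer that the two cut-offs contradict each other, but they need not match. The gap is that no other row receives the post-dose results.
- **Listing only.** A reader might infer that an abnormality tied to discontinuation would be seen only in a listing. The documents do not support that, because the adverse-event criteria and the 30-day period bring such findings into the adverse-event tables. They arrive as terms, however, not as values, shifts or QTcF categories.
- **Bias toward normal.** A reader might infer that the dropped results come mainly from safety stops and so make the tables look too clean. This is not established. Subjects on 50 or 100 mg have no taper whatever their reason for leaving, and follow-up results are dropped for all who leave. A value that prompted a stop may well have been taken before it and so be admitted.
- **Timing.** Protocol 9.3.7 places the assessments at the time of termination, and a visit on the last dose day is kept. The instruction to come in as soon as possible (9.3.9) covers only discontinuation after the first year. Not every untapered stop therefore loses its results.
- **Low stakes.** The extension analysis is descriptive (SAP 11.1), and the table shells are a separate document not available here. Both are fair limits, but the SAP text defines no termination or follow-up row for the shells to implement.

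**Conclusion.** The point holds as a reporting gap. Under the SAP as written, every laboratory and vital-sign result from the planned 14-day follow-up, and every termination-visit result dated at least one day after the last dose, is absent from the summary, shift and QTcF/heart-rate threshold tables. For laboratory shifts this also conflicts with what 11.3.2 sets out to show.

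The loss is confined to values, shifts and threshold categories. Its size and direction cannot be computed, because the documents do not say how many subjects stop without a taper or how soon they are then seen.

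The conclusion rests on reading footnote [2] literally and on the absence of any further rule in the unseen table shells. It also takes the last dose day to include taper doses, which the SAP should state. If taper doses do not count, more results could be lost.

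The half-life calculation supports reporting values from the first few days after the last dose. It does not support extending the numbered windows to 14 or 30 days, which would mix essentially off-drug values into on-treatment visits.

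**What to change.** Keep footnote [2] for the numbered on-treatment visits, state whether taper doses count toward the last dose day, and add two rows to Appendix 2:

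1. **End of treatment/early termination** in 14.1, 14.2 and 14.3. It takes the termination-visit result even when dated after the last dose, within a short stated limit that ends before follow-up. With the ±3-day allowance on Visit 17, a visit due at +14 days can fall at 14 − 3 = +11, so the limit should be no later than +10 days. Include this row in the shift tables and in the QTcF and heart-rate threshold counts, and label it as possibly a few days off drug.
2. **Follow-up (last dose + 14 days)** in 14.2 and 14.3 only, since no ECG is scheduled then. Identify it by the protocol's Visit 17, and relabel the day-575 vital-sign row so that the two are not confused.

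The cost is SAP wording and two extra table rows, with no new data. Some termination values will be a few days off drug, which the label discloses. SAP Section 4 allows revision before the extension database lock.

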14.2 Clinical Laboratory Assessments

The following visit windows will be applied for reporting **clinical laboratory** open-label extension results:

Analysis Timepoint	C017 OLE	
I IIII Openii	Target Study Day [1]	Window [2]
		Study Days
Baseline	1	<= 1
Start of OLE [3] – Visit 9	127	>= 113 to <= 141
Visit 12	155	>=142 to <= 239
Visit 14	323	>=240 to <=407
Visit 16	491	>=408 to <= 575
Visit 18	659	>=576 to <=743
Visit 20	827	>=744 to <=911
Visit 22	995	>=912 to <=1079
Visit 24	1163	>= 1080 to <=1247
Visit 26	1331	>= 1248 to <=1415
Visit 28	1499	>=1416 to <=1583
Visit 30	1667	>=1584 to <=1751
Visit 32	1835	>=1752 to <=1919
Visit 34	2003	>=1920 to <=2087
Visit 36	2171	>=2088 to <=2255
Visit 38	2339	>=2256 to <=2423
Visit 40	2507	>=2424 to <=2591

Visit 42	2675	>=2592 to <=2756
Visit 44 [4]	2843	>=2760

OLE=Open-label Extension

- [1] Relative to the date of the first dose of study drug. For example, Day 1 = the date of the first dose of study drug.
- [2] The study days evaluated for windows of visits during treatment period are on or prior to the last dose day.
- [3] This window should include the study day when the first dose of OLE study medication was given.
- [4] Expected timepoint C017 OLE.

14.3 Vital Sign Assessments

The following visit windows will be applied for reporting **vital signs** open-label extension results:

Analysis Timepoint	C017 OLE	
I IIII Openii	Target Study Day [1]	Window [2]
		Study Days
Baseline	1	<= 1
Start of OLE [3] – Visit 9	127	>= 120 to <=134
Visit 11	141	>=135 to <=148
Visit 12	155	>=149 to <=197
Visit 13	239	>=198 to <=281
Visit 14	323	>=282 to <=365
Visit 15	407	>=366 to <=449
Visit 16	491	>=450 to <=533
Visit 17	575	>=534 to <=617
Visit 18	659	>=618 to <=701
Visit 19	743	>=702 to <=785
Visit 20	827	>=786 to <=869
Visit 21	911	>=870 to <=953
Visit 22	995	>=954 to <=1037
Visit 23	1079	>=1038 to <=1121
Visit 24	1163	>=1122 to <=1205
Visit 25	1247	>=1206 to <=1289

Visit 26	1331	>=1290 to <=1373
Visit 27	1415	>=1374 to <=1457
Visit 28	1499	>=1458 to <=1541
Visit 29	1583	>=1542 to <=1625
Visit 30	1667	>=1626 to <=1709
Visit 31	1751	>=1710 to <=1793
Visit 32	1835	>=1794 to <=1877
Visit 33	1919	>=1878 to <=1961
Visit 34	2003	>=1962 to <=2045
Visit 35	2087	>=2046 to <=2129
Visit 36	2171	>=2130 ro <=2213
Visit 37	2255	>=2214 to <=2297
Visit 38	2339	>=2298 to <=2381
Visit 39	2423	>=2382 to <=2465
Visit 40	2507	>=2466 to <=2549
Visit 41	2591	>=2550 to <=2633
Visit 42	2675	>=2634 to <=2717
Visit 43	2759	>=2718 to <=2801
Visit 44 [4]	2843	>=2802

OLE=Open-label Extension

^[1] Relative to the date of the first dose of study drug. For example, Day 1 = the date of the first dose of study drug.

^[2] The study days evaluated for windows of visits during treatment period are on or prior to the last dose day.

^[3] This window should include the study day when the first dose of OLE study medication was given.

^[4] Expected timepoint C017 OLE.

